7.1.7 Withdrawal of consent

Subjects may voluntarily withdraw consent to participate in the study for any reason at any time. Withdrawal of consent occurs only when a subject:

- Does not want to participate in the study anymore, and
- Does not allow further collection of personal data

In this situation, the investigator should make a reasonable effort (e.g. telephone, e-mail, letter) to understand the primary reason for the subject's decision to withdraw his/her consent and record this information.

Study treatment must be discontinued and no further assessments conducted, and the data that would have been collected at subsequent visits will be considered missing.

Further attempts to contact the subject are not allowed unless safety findings require communicating or follow-up.

All efforts should be made to complete the assessments prior to study withdrawal. A final evaluation at the time of the subject's study withdrawal should be made as detailed in the assessment table.

Novartis will continue to keep and use collected study information (including any data resulting from the analysis of a subject's samples until their time of withdrawal) according to applicable law.

For US and Japan: All biological samples not yet analyzed at the time of withdrawal may still be used for further testing/analysis in accordance with the terms of this protocol and of the informed consent form.

For EU and Rest of World: All biological samples not yet analyzed at the time of withdrawal will no longer be used, unless permitted by applicable law. They will be stored according to applicable legal requirements.

7.2 Assessment types

7.2.1 Efficacy assessments

7.2.1.1 Molecular response

Molecular response (MR) will be assessed in all patients randomized to each treatment arm as well as in patients that switch study treatment from bosutinib to asciminib.

Levels of BCR-ABL1 transcripts will be determined by real-time quantitative PCR (RQ-PCR) testing of peripheral blood and analyzed at a central testing laboratory. Log reduction in BCR-ABL1 transcripts levels from the standardized baseline value, or the percent ratio of BCR-ABL1 transcripts versus control gene (ABL) transcripts converted to a reference standard, international scale ([Hughes and Branford 2006](#)), will be calculated for each sample.

Major molecular response and related variables are defined as the following:

- Rate of Major Molecular Response (MMR) where MMR is defined as a ≥ 3.0 log reduction in BCR-ABL1 transcripts compared to the standardized baseline equivalent to ≤ 0.1 % BCR-ABL1/ABL % by international scale as measured by RQ-PCR, confirmed by duplicate analysis of the same sample
- Time to MMR defined as the time from the date of randomization to the date of the first documented MMR,
- Duration of MMR defined as the time from the date of first documented MMR to the earliest date of loss of MMR, progression to AP or BC, or CML-related death.

Loss of MMR is defined as increase of BCR-ABL1/ABL to > 0.1% by international scale (IS) in association with a ≥ 5 -fold rise in BCR-ABL1 from the lowest value achieved on study treatment and replicated by a second analysis of the same sample. Loss of MMR must be confirmed by subsequent sample analysis within 4 to 6 weeks showing loss of MMR associated with a ≥ 5 -fold rise in BCR-ABL1 from the lowest value achieved on study treatment, unless it is associated with confirmed loss of CHR or loss of CCyR or progression to AP/BC or CML-related death. Mutational analysis will be performed at a Novartis designated laboratory by Sanger sequencing at Week 1 Day 1, upon confirmed loss of MMR and/or at end of treatment. If the result at Week 1 Day 1 is positive for a mutation, analysis will be performed every 12 weeks.

The blood samples will be taken as described in [Table 7-1](#), [Table 7-2](#) and [Table 7-3](#).

Table 7-3 Blood samples (efficacy primary endpoint)

Sample Type	Volume	Visit	Time point
Blood for BCR-ABL1 quantification by RQ-PCR	20 mL	Screening/Baseline / S-Screening/S-Baseline*	Pre-dose
	20 mL	Week 4 / S-Week 4	Pre-dose
	20 mL	Week 8 / S-Week 8	Pre-dose
	20 mL	Week 12 / S-Week 12	Pre-dose
	20 mL	Week 16 / S-Week 16	Pre-dose
	20 mL	Week 24 / S-Week 24	Pre-dose
	20 mL	Week 36 / S-Week 36	Pre-dose
	20 mL	Week 48 / S-Week 48	Pre-dose
	20 mL	Week 60 / S-Week 60	Pre-dose
	20 mL	Week 72 / S-Week 72	Pre-dose
	20 mL	Week 84 / S-Week 84	Pre-dose
	20 mL	Week 96 / S-Week 96	Pre-dose
	20 mL	Every 12 weeks thereafter up to end of study treatment	Pre-dose
20 mL	End of Treatment / S-End of Treatment	Anytime	
Blood for BCR-ABL1 Mutation analysis by Sanger Sequencing	5 mL	Week 1 Day 1 /S-Week 1 Day 1*	Pre-dose
	No sample collected - testing is performed on the "Blood for BCR-ABL1 quantification by RQ-PCR" sample	Upon confirmed loss of MMR and/or End of Treatment/ S-End of Treatment	Anytime
Blood for BCR-ABL1 Mutation analysis only for patients with mutations at Week 1 Day 1	No sample collected - testing is performed on the "Blood for BCR-ABL1 quantification by RQ-PCR" sample	Week 12 and every 12 weeks thereafter up to end of study treatment	Anytime

*Assessment does not need to be completed during the visit for patients in the treatment switch if already collected during the EOT or the treatment switch screening visit.

During the study, peripheral blood samples will be collected into PAXgene™ Blood RNA tubes for all RQ-PCR assessments. Detailed instructions for the collection, handling, and shipment of RQ-PCR and mutation samples are outlined in the [\[CABL001A2301 Laboratory Manual\]](#).

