spontaneous miscarriage or in the event of elective abortion, the patient is permitted to continue study treatment.

- In the event of treatment failure the patient must be discontinued from the study treatment. Patients randomized to bosutinib treatment experiencing treatment failure may switch to asciminib treatment. The following events will constitute ‘treatment failure’, and are based on the ELN criteria ([Baccarani et al 2013](#)) defining failure of a second line treatment:
 - No CHR or > 95% Ph+ metaphases at three months after initiation of therapy or thereafter
 - BCR-ABL1 ratio > 10% IS and/or > 65% Ph+ metaphases at six months after initiation of therapy or thereafter
 - BCR-ABL1 ratio > 10% IS and/or > 35% Ph+ metaphases at 12 months after initiation of therapy or thereafter
 - Loss of CHR, CCyR or PCyR at any time after initiation of therapy
 - Detection of new BCR-ABL1 mutations which potentially cause resistance to study treatment (asciminib or bosutinib) at any time after initiation of therapy
 - Confirmed loss of MMR in 2 consecutive tests ([Section 7.2.1.1](#))
 - New clonal chromosome abnormalities in Ph+ cells: CCA/Ph+: at any time after initiation of therapy
- In the event of disease progression the patient must be discontinued from the study treatment. The following events are considered disease progression.
 1. CML-related death (any death during treatment or follow-up if the principal cause of death is marked as “study indication” in the eCRF by the investigator, or if the death occurred subsequent to documented progression to AP/BC and the cause of death is reported as “unknown” or not reported by the investigator)
 2. Accelerated phase (AP) as defined by any of the following:
 - $\geq 15\%$ blasts in the peripheral blood or bone marrow aspirate, but $< 30\%$ blasts in both the peripheral blood and bone marrow aspirate
 - $\geq 30\%$ blasts plus promyelocytes in peripheral blood or bone marrow aspirate
 - $\geq 20\%$ basophils in the peripheral blood
 - Thrombocytopenia ($< 100 \times 10^9/L$) that is unrelated to therapy
 3. Blast crisis (BC) as defined by any of the following:
 - $\geq 30\%$ blasts in peripheral blood or bone marrow aspirate
 - Appearance of extramedullary involvement other than hepatosplenomegaly proven by biopsy (i.e., chloroma).

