10.5.2 Other secondary efficacy objectives

Unless otherwise stated the FAS will be used for the analysis of all other secondary efficacy endpoints. The exceptions are using the Molecular Responder Set for duration of MMR and time to MMR, the CCyR Analysis Set for CCyR rates, and the Cytogenetic Responder Set for duration of CCyR and time to CCyR.

No statistical testing of non-key secondary efficacy endpoints will be performed, and any analysis will be considered exploratory.

[figure not shown]
Molecular Response

MMR rates at scheduled time points (except 24 and 96 weeks which have been specified as primary and key secondary endpoints) will be evaluated in a similar fashion to the primary analysis of MMR rate at 24 weeks. Patients discontinuing the randomized treatment prior to a specific time point due to any reason will be considered as non-responders for that time point.

MMR rates by scheduled time points are defined as the proportion of patients who achieve MMR at or before the specified visit, i.e. if a patient achieves an MMR but then loses it before or at the visit, he/she will still be classed as achieving MMR by that time point.

For each endpoint the rate and the associated 95% confidence interval based on the Pearson-Clopper method will be presented by treatment group. Confidence intervals for the differences in any response rates between treatment groups will be provided using the Wald method.

Statistical testing will be performed via CMH chi-square tests stratified by the randomization strata. The Mantel-Haenszel estimate of the common risk difference and the corresponding 95% confidence interval will also be provided.

Duration of MMR is defined in [Section 7.2.1.1](#) as the time between the date of the first documented MMR and the earliest date of loss of MMR, progression to AP/BC, or CML-related death for patients in the Molecular Responder Set. The time will be censored at the last molecular assessment (PCR) date while on treatment for patients who have not experienced any of the above events.

Duration of MMR will be analyzed by K-M method and presented by K-M plots. The estimated rates of patients who are still responding at various time points will also be provided using K-M method.

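### An isolated loss of MMR first seen at EOT, or rechecked only outside 4 to 6 weeks, is on a literal reading censored, which biases the exploratory Kaplan-Meier duration of MMR upward

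*Combined protocol and SAP*

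**What the plan says.** Section 7.2.1.1 gives the threshold, "Loss of MMR is defined as increase of BCR-ABL1/ABL to > 0.1% by international scale (IS) in association with" at least a 5-fold rise from the lowest on-treatment value, replicated on the same sample. It then adds: "Loss of MMR must be confirmed by subsequent sample analysis within 4 to 6 weeks". A second sample is not needed in four situations: "unless it is associated with confirmed loss of CHR or loss of CCyR or progression to AP/BC or CML-related death".

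Duration of MMR runs from first MMR to the "earliest date of loss of MMR, progression to AP or BC, or CML-related death". Section 10.5.2 repeats these events and adds: "The time will be censored at the last molecular assessment (PCR) date while on treatment for patients who have not experienced any" of them. The analysis is Kaplan-Meier, with estimated rates still responding at various times. Section 10.5.2 classes non-key secondary endpoints as exploratory, without formal testing.

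Table 7-3 schedules RQ-PCR at Weeks 4, 8, 12, 16 and 24, then at 12-week steps to Week 96, then "Every 12 weeks thereafter up to end of study treatment", with a last sample at EOT. Section 7.1.6 limits follow-up after EOT to survival, later therapies, transplant and progression.

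The wording of the event varies. Sections 7.2.1.1 and 10.5.2 (duration of MMR) speak of loss. Section 10.5.2 (time to treatment failure, TTF) speaks of confirmed loss. Section 7.1.6 has "Confirmed loss of MMR in 2 consecutive tests", with a cross-reference to 7.2.1.1. Section 7.1.2.2 uses the same two-test wording without the cross-reference.

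**The concern.** A Kaplan-Meier estimate is sound when censored patients have the same prospects as those who remain. A patient censored at the sample that shows loss of response is the opposite case, because the censoring is caused by the event. Each such patient leaves the risk set as a continuing responder, and the curve stays too high.

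What is at stake is the reported durability of response. It also matters that two programmers could derive different durations from the same data, because the plan does not say whether the duration event needs confirmation, or what happens when confirmation is absent or late.

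**Working it through.** **The plan's own figure.** The documents give none for duration of MMR, so there is nothing to reproduce on this point. For context, the sample size does reproduce: 15% versus 35%, two-sided 5%, 2:1, pooled variance and no continuity correction give 74 + 148 = 222, with power 90.3%.

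**Step 1: can a scheduled PCR confirm a loss?** Visit weeks come from Table 7-3 and visit windows from Section 7.1.5. The confirmation window is 28 to 42 days.

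| Loss seen at | Next scheduled PCR | Gap | Shortest gap using visit windows | Within 42 days? |
|---|---|---|---|---|
| Week 8 or 12 | 4 weeks later | 28 days | not needed | yes, nominally at day 28 |
| Week 16 | Week 24 | 56 days | 56 − 1 − 2 = 53 days | no |
| Weeks 24 to 84 | 12 weeks later | 84 days | 84 − 2 − 2 = 80 days | no |
| Week 96 | Week 108 | 84 days | 84 − 2 − 7 = 75 days | no |
| After Week 96 | 12 weeks later | 84 days | 84 − 7 − 7 = 70 days | no |

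From Week 16 on, only an extra sample, or an EOT sample that happens to fall in the window, can confirm a loss.

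**Step 2: is the extra sample provided for?** Tables 7-1 and 7-10 name a visit to confirm loss of MMR, but attach it to the low-level mutation sample. Neither Table 7-1 nor Table 7-3 lists an RQ-PCR there. In Table 7-1 the safety and survival follow-up columns have no RQ-PCR.

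**Step 3: literal outcome for duration of MMR.**

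| Course | Outcome if loss must be confirmed as in 7.2.1.1 |
|---|---|
| Loss, second sample at 4 to 6 weeks also shows loss | event |
| Loss with one of the four exceptions | event, no second sample needed |
| Isolated loss first seen at EOT | no later PCR on randomized treatment; censored at the EOT sample that shows the loss |
| Isolated loss, rechecked only outside 4 to 6 weeks | no rule given; literally unconfirmed, so censored at the last on-treatment PCR |

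**Step 4: size, under assumptions.** Suppose a constant share u of true losses is censored at the time of loss. The estimated cumulative hazard is then (1 − u) times the true one, so S_est = S_true^(1 − u). For example, 0.80^0.75 = 0.846.

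| True proportion in MMR at 72 weeks | u = 10% | u = 25% | u = 50% |
|---|---|---|---|
| 90% | 91.0% | 92.4% | 94.9% |
| 80% | 81.8% | 84.6% | 89.4% |
| 70% | 72.5% | 76.5% | 83.7% |

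The overstatement runs from 1.0 to 13.7 points. A simulation on a 12-week visit grid agreed within 0.2 points. Both u and the true proportions are assumptions.

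**Step 5: how few patients it takes.** Planned responders at Week 24 are 0.35 × 148 = 51.8 on asciminib and 0.15 × 74 = 11.1 on bosutinib. With 11 responders, one uncounted loss is 1/11 = 9.1 points as a crude proportion. The responder set includes anyone reaching MMR at any time, so the final numbers may be larger.

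**The case against.** The strongest reply is that the 4-to-6-week sentence instructs sites to take a sample and does more than filter the data. The confirmation visit appears in the schedule, and Table 7-3 runs Sanger sequencing at confirmed loss on the RQ-PCR sample, which presupposes that such a sample exists. This stands. A reader might infer that the 12-week schedule itself blocks confirmation. The documents do not support that: before Week 16 scheduled samples are 4 weeks apart, and later a recheck outside the window means that a required sample was missed or late.

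The exceptions also have force at EOT, where hematology, extramedullary assessment and a marrow aspirate are scheduled, so some losses at EOT count without a second PCR. They do not cover every case. Loss of MMR begins just above 0.1% IS, while CCyR is read on a minimum of 20 metaphases, so a molecular loss need not show there.

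Duration of MMR is worded with loss, not confirmed loss, so one may argue that unconfirmed losses already count. That is possible, but the definition it relies on carries the confirmation requirement. The reply therefore shows ambiguity and does not resolve it.

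A reader might infer that Section 7.1.6 contradicts Section 7.2.1.1. Because 7.1.6 cross-refers to 7.2.1.1, that is weak. Section 7.1.2.2, which lacks the cross-reference, is the looser text.

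A reader might also infer that the bias differs by arm, since confirmed loss opens a switch only for bosutinib patients in an open-label trial. That gives a possible motive for more diligent rechecking in one arm, but the documents hold no evidence of it.

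**Conclusion.** The concern holds in limited form. Read literally, the confirmation rule, the PCR schedule and the censoring rule together censor an isolated loss first seen at EOT, and one rechecked only outside the window. The direction is upward for the Kaplan-Meier duration of MMR. The size cannot be derived from the documents: the 1.0 to 13.7 points above rest on assumed values of u and of the true proportion, and the bias is zero if every loss is confirmed in time or meets an exception.

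Only a non-key exploratory endpoint is touched. A reader might infer that the main efficacy result is at risk. It is not: MMR at Weeks 24 and 96 is judged against the 0.1% threshold at the visit, with no use of the loss rule. TTF is protected for losses at EOT, because stopping randomized treatment for any reason is already a TTF event.

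Only part of the combined document was available, so a derivation rule elsewhere in the SAP may already settle the point.

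**What to change.** 1. In the SAP, for duration of MMR, date the event at the first loss when the next available PCR at least 4 weeks later also shows loss, even if it falls after 6 weeks.
2. For losses with no later PCR because treatment stopped, report duration of MMR twice: with these losses as events, and under the strict 4-to-6-week rule.
3. List in Tables 7-1 and 7-3 the confirmatory RQ-PCR that Section 7.2.1.1 already requires.
4. Reconcile the loss wording (7.2.1.1, and 10.5.2 for duration of MMR) with confirmed loss (10.5.2 for TTF) and two consecutive tests (7.1.2.2, 7.1.6). Which wording should govern stopping or switching is a clinical matter and is left open here.

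Cost: items 1 and 2 are derivation changes. Items 3 and 4 alter protocol text and so need an amendment under Section 12.1, but add no sampling beyond what the text already demands. The downside is that a transient rise, for example after a dose hold just before stopping, may count as a loss in one of the two analyses. For that reason, unconfirmed losses at EOT are better shown both ways than made events in a single main analysis.

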7.2.1.2 Bone marrow analysis and cytogenetics

Cytogenetic response will be assessed locally as the percentage of Ph+ metaphases in the bone marrow and is defined as the following (a review of a minimum of 20 metaphases is required):

- Complete (CCyR) - 0% Ph+ metaphases
- Partial (PCyR) - >0 to 35% Ph+ metaphases
- Major (MCyR) - 0 to 35% Ph+ metaphases
- Minor (mCyR) - >35 to 65% Ph+ metaphases
- Minimal - >65 to 95% Ph+ metaphases
- None - >95 to 100% Ph+ metaphases.

Bone marrow aspirate for cytogenetic analyses will be performed at screening/baseline (performed up to 56 days prior to Week 1 Day 1), at Week 24/S-Week 24, 48/S-48, 72/S-72, 96/S-96 as long as patient has not achieved MMR and at end of treatment (S-end of treatment as specified in [Table 7-1](#) and [Table 7-2](#). For patients on the bosutinib arm an unscheduled bone marrow assessment at week 12 may be performed to evaluate cytogenetic response in consideration for potential dose escalation.

Quantification of the percentage of Ph+ chromosome metaphases, number of metaphases, number positive for Ph chromosome, additional chromosomal abnormalities as well as data from cytologic evaluation (microscopic analysis) of percentage of blasts and promyelocytes will be recorded on the Bone Marrow eCRF. These exams will be performed and analyzed locally. Fluorescent In-situ hybridization (FISH) analysis will not be accepted.

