6.2 Dose escalation guidelines

Dose escalation beyond the standard doses of 40 mg BID for asciminib is not permitted.

Dose escalation above 500 mg QD for bosutinib is permitted in this study. Bosutinib escalation guidelines are as follows:

Consider dose escalation to 600 mg once daily in patients who are currently taking 500 mg daily, did not have Grade 3 or higher adverse events and who:

- Did not reach complete hematological response (CHR) by week 8
- Did not reach complete cytogenetic response (CCyR) by week 12

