The cumulative incidence of MMR will be graphically displayed by an increasing step function. This curve will increase each time (after randomization) at which a new responder is observed and thus will increase up to the best observed response rate (e.g. up to 50% if half of the patients in the analysis population are able to achieve response).

Time to MMR is defined in [Section 7.2.1.1](#) and calculated as: date of first MMR - date of randomization +1, for patients in the Molecular Responder Set. Descriptive statistics (minimum, maximum, median, quartiles, mean, sd) of time to MMR will be provided for the two treatment groups separately.

Cytogenetic Response

Patients in FAS will be categorized with counts and percentages provided for cytogenetic response (Complete, Partial, Major, Minor, Minimal, No Response) at and by (i.e. best response up to a specified time point) scheduled time points. Shift tables will also be employed to examine the changes in cytogenetic response category from baseline.

Since there are expected to be only limited numbers who are actually in CCyR at baseline the analysis of CCyR rate at and by scheduled time points will only include patients who are not in CCyR at baseline, i.e. the CCyR Analysis Set.

CCyR rates at and by scheduled time points etc. and the associated 95% confidence intervals based on the Pearson-Clopper method will be presented by treatment group with the analysis of these endpoints only including patients who are not in CCyR at baseline.

Confidence intervals for the differences in any response rates between treatment groups will be provided using the Wald method.

Statistical testing will be performed via CMH chi-square tests stratified by the randomization strata. The Mantel-Haenszel estimate of the common risk difference and the corresponding 95% confidence interval will also be provided.

Time to CCyR is defined for patients in the Cytogenetic Responder Set as: date of first CCyR - date of randomization +1. Descriptive statistics (minimum, maximum, median, quartiles, mean, sd) of time to CCyR will be provided for the two treatment groups separately.

The cumulative incidence of CCyR will also be graphically displayed by an increasing step function. This curve will increase each time (after randomization) at which a new responder is observed and thus will increase up to the best observed response rate.

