Duration of CCyR is defined as the time between date of first documented CCyR and the earliest date of loss of CCyR, progression to AP/BC, or CML-related death for patients in the

Cytogenetic Responder Set. The time will be censored at the last cytogenetic assessment date on treatment for patients for whom none of the above events is reported or last PCR evaluation on treatment indicating MMR.

Duration of CCyR response will be analyzed by K-M method and presented by K-M plots. The estimated rates of patients who are still responding at various time points will also be provided using K-M method.

Treatment failure, disease progression and survival

Time to treatment failure (TTF) is defined as the time from date of randomization to an event of treatment failure. The following events will constitute ‘treatment failure’, and are based on the ELN criteria ([Baccarani et al 2013](#)) defining failure of a second line treatment adapted to include discontinuation of randomized treatment as an event:

- No CHR or > 95% Ph+ metaphases at three months after randomization or thereafter
- BCR-ABL1 ratio > 10% IS and/or > 65% Ph+ metaphases at six months after randomization or thereafter
- BCR-ABL1 ratio > 10% IS and/or > 35% Ph+ metaphases at 12 months after randomization or thereafter
- Loss of CHR, CCyR or PCyR at any time after randomization
- Detection of new BCR-ABL1 mutations which potentially cause resistance to study treatment at any time after randomization
- Confirmed loss of MMR
- New clonal chromosome abnormalities in Ph+ cells: CCA/Ph+: at any time after randomization
- Discontinuation from randomized treatment for any reason

[figure not shown]
For patients who have not reached treatment failure, their TTFs will be censored at the time of last study assessment (PCR, cytogenetic, hematologic or extramedullary) before the cut-off date.

Progression-Free-Survival (PFS) is defined as the time from the date of randomization to the earliest occurrence of documented disease progression to AP/BC or the date of death from any cause (including progressions and deaths observed during the survival follow-up period) before the cut-off date.

The time will be censored at the date of last study assessment (PCR, cytogenetic, hematologic or extramedullary) or last post-treatment follow-up for patients without event.

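### An optional Week 12 marrow is provided for bosutinib only and the CCyR definitions do not exclude it, so first-CCyR dates are not comparable between arms

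*Combined protocol and SAP*

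**What the plan says.** Section 7.2.1.2 places the on-treatment cytogenetic marrows, in both arms, "at Week 24/S-Week 24, 48/S-48, 72/S-72, 96/S-96 as long as patient has not achieved MMR", with one more at end of treatment (EOT). It then makes one arm-specific provision: "For patients on the bosutinib arm an unscheduled bone marrow assessment at week 12 may be performed to evaluate cytogenetic response". The stated purpose is the bosutinib dose-escalation decision. One of the criteria in section 6.2 is "Did not reach complete cytogenetic response (CCyR) by week 12". The same section says for the other arm: "Dose escalation beyond the standard doses of 40 mg BID for asciminib is not permitted".

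Section 10.5.2 defines the cytogenetic endpoints as follows:

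- Response categories are reported "at and by (i.e. best response up to a specified time point) scheduled time points".
- "Time to CCyR is defined for patients in the Cytogenetic Responder Set as: date of first CCyR - date of randomization +1".
- "Duration of CCyR is defined as the time between date of first documented CCyR and the earliest date of loss of CCyR", or progression or CML-related death if earlier.
- The cumulative incidence curve steps up whenever a new responder is seen.

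The Cytogenetic Responder Set in 10.1.6 admits a patient with CCyR at any time on study treatment who was not in CCyR at baseline. For PCR, sections 10.4.3 and 10.5.1.1 say how unscheduled results are used. The sections cited here contain no matching rule for unscheduled marrows.

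**The concern.** The date of first CCyR depends on when someone looks. If one arm has an extra look halfway to the other arm's first scheduled look, and the definitions accept it, recorded onset differs between arms even when true onset does not. Time to CCyR, duration of CCyR and cytogenetic response 'by' each time point are listed in sections 3 and 10.5 as secondary endpoints for comparing asciminib with bosutinib. A reader of the study report would take a difference in them as a property of the drugs.

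**Working it through.** **Plan's own figure.** The documents give no figure for the CCyR endpoints. The one relevant input is the planned arm size. Section 10.8 assumes 15% v 35%, two-sided 5%, 90% power and 2:1 allocation. With pooled variance and no continuity correction, the pooled rate is (0.15 + 2×0.35)/3 = 0.2833. The bosutinib arm then needs [1.96√(1.5×0.2833×0.7167) + 1.2816√(0.15×0.85 + 0.35×0.65/2)]² / 0.20² = 73.2, so 74, and 222 in total. This matches the plan. It concerns MMR by PCR and does not depend on marrow timing.

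**Looks provided for.** By Week 24: bosutinib 2 (Weeks 12 and 24), asciminib 1 (Week 24). By Week 96: 5 v 4. EOT marrows are extra in both arms.

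**Largest gap for one patient.** 24 − 12 = 12 weeks, when the asciminib patient is first examined at Week 24. It can be longer for a patient in MMR before Week 24, who has no scheduled marrow until EOT. Section 10.5.2 uses MMR only in censoring CCyR duration, not to credit a CCyR.

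**Mean shift among patients with CCyR by Week 24.** Let q be the share of them already in CCyR at Week 12, and u the share of those who have the Week 12 marrow. With equal efficacy and sustained response, the shift is 12×u×q weeks. Neither u nor q is in the documents, so both are assumptions:

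- u = 0.25, q = 0.5: 1.5 weeks
- u = 0.5, q = 0.5: 3 weeks
- u = 1, q = 0.5: 6 weeks
- u = q = 1: 12 weeks (upper limit)

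**All responders to Week 96.** Assume a constant CCyR hazard with 20% in CCyR by Week 24. Section 1.2.2 cites 27% with major cytogenetic response by Week 24 on bosutinib after at least two TKIs. CCyR is part of that category, so 20% is not above the plan's own source.

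- New responders at Weeks 24, 48, 72 and 96: 20, 16, 12.8 and 10.24 points, total 59.04.
- Mean time without the extra marrow: (20×24 + 16×48 + 12.8×72 + 10.24×96)/59.04 = 53.4 weeks.
- In CCyR by Week 12: 1 − √0.8 = 10.56 points.
- Shift at full uptake: 12×10.56/59.04 = 2.1 weeks, giving a mean of about 51.2. At half uptake the mean is about 52.3.
- Median: 20/59.04 = 34% of responders are dated by Week 24 and 36/59.04 = 61% by Week 48, so it is Week 48 with or without the extra marrow.
- Lower quartile: at full uptake 10.56/59.04 = 18% are dated Week 12, so it stays at Week 24.

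**CCyR 'by' Week 24.** A sustained response found at Week 12 would also be found at Week 24, so the rate does not change. It rises only for a Week 12 CCyR that is lost, missing, off treatment, or not re-examined because of MMR by Week 24. Each such patient adds 1/74 = 1.35 points, slightly more in the CCyR Analysis Set, which leaves out patients in CCyR at baseline. For scale, at 20% in each arm the Wald 95% half-width for the difference is 1.96√(0.2×0.8×(1/74 + 1/148)) = 11.2 points.

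**Duration of CCyR.** An earlier start lengthens recorded duration for a sustained response. The Week 12 look also admits short responses lost before Week 24, which shortens it. The net sign cannot be derived from the documents.

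**With the change below.** The part of the gap due to the Week 12 marrow is 0 weeks.

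**The case against.** The strongest reply has four parts.

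- **Inference from silence.** No sentence says that unscheduled marrows count. This stands as a caution: a derivation rule in a part of the SAP not available here would settle the point. The definitions that are available carry no limit, though, and 'scheduled time points' in 10.5.2 names the reporting times, not the marrows that are eligible.
- **Asciminib marrows before Week 24 are possible.** Nothing forbids them, and section 7.1.6 makes more than 95% Ph+ metaphases at three months a failure criterion in both arms. A reader might infer that an asciminib CCyR cannot be documented before Week 24. That is too strong: an unscheduled or EOT marrow could do it. What remains is that only bosutinib has a named provision and a reason tied to CCyR at Week 12.
- **Uptake is probably low among responders.** The marrow is optional and serves an escalation decision, and PCR at Weeks 4, 8 and 12 may direct it to suspected poor responders. This stands, and it argues for the lower values of u.
- **Little turns on it.** Section 10.5.2 makes these endpoints exploratory without testing, although it then specifies CMH tests for CCyR rates. Time to CCyR is summarised within each arm among responders. Any shift in it favours the comparator, so it does not flatter asciminib. This limits the importance but does not make the onset dates comparable.

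**Conclusion.** The concern holds in limited form. Followed as written, the plan gives unequal ascertainment of first CCyR. Time to CCyR, the cumulative incidence curve and the start of CCyR duration are not comparable between arms, with a gap of up to 12 weeks for a patient whose asciminib counterpart is first examined at Week 24. The average effect may be small. In the 20% illustration, the all-responder mean moves by about 2 weeks at full uptake and the median does not move. Those figures rest on assumed uptake, a constant hazard and sustained response.

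A reader might infer that two identical drugs would show faster and longer CCyR, and higher 'by' rates, on bosutinib. The documents do not support that as a general statement: the summary median may be unchanged, 'by' rates move only for a Week 12 CCyR not documented at Week 24, and the sign for duration is uncertain. Nor should the point be carried to the primary or key secondary endpoint. MMR at 24 and 96 weeks is PCR-based and is not directly affected. This is a worthwhile clarification of non-key secondary endpoints.

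**What to change.** In section 10.5.2, state that the main derivation of CCyR 'by' rates, time to CCyR, the cumulative incidence curve and the start of CCyR duration uses marrow visits planned in both arms (Weeks 24, 48, 72, 96 and EOT). Apply the rule to unscheduled marrows in either arm. List the unscheduled marrows and repeat the derivations with all marrows as a sensitivity analysis. If the intention was already to leave out the Week 12 result, one sentence saying so is enough.

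The cost is a few words and a small number of valid unscheduled results left out of the main derivation. No procedure, dose rule or sample size changes. The change removes the Week 12 asymmetry only. EOT timing may still differ by arm, and marrows omitted because of MMR remain omitted.
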